## Statistical Analysis Plan

### 1 SYNOPSIS OF STUDY DESIGN

#### 1.1 Purpose of the Statistical Analysis Plan

This statistical analysis plan (SAP) is intended to provide a detailed and comprehensive description of the planned methodology and analysis to be used for Clinical Investigation Plan [REDACTED] the CONFIDENCE clinical investigation. [REDACTED]

#### 1.2 Clinical Investigation Objectives

The objective of this registry is to characterize the procedural safety and device performance of the Portico™ valve from experienced TAVI centers that commercially use the Portico™ valve, delivery system and loading system to treat patients with severe aortic stenosis.

#### 1.3 Clinical Investigation Design

The CONFIDENCE Registry is a prospective, non-randomized, observational, single-arm, multicenter registry of patients clinically indicated for implantation of a Portico™ transcatheter aortic heart valve. The registry has broad inclusion criteria (symptomatic degenerative aortic stenosis) and minimal exclusion criteria to ensure the results are generalizable to the broadest TAVI population. Approximately 1000 subjects from up to 50 centers will undergo transcatheter aortic valve replacement (independent of valve size) using a commercially available Portico™ valve and transfemoral delivery system. No center may enroll more than 10% of total subjects (100) and maximum 50 subjects in each half of the study.

In order to evaluate the current generation product to the next generation, the total enrollment in the CONFIDENCE Registry will consist of approximately 500 subjects treated with the first generation Portico delivery system (Models PRT-DS-TF-18F/19F) and 500 with the next generation FlexNav delivery System (Models FN-DS-SM/LG).

Subjects will undergo prospective enrollment with baseline data collection prior to receiving their Portico Valve (up to a maximum of 180 days prior to the Portico valve implant procedure). The implant procedure will be conducted per standard protocol established at each center. After the procedure, subjects will undergo a pre-discharge visit at the time of hospital discharge or within seven days of the index procedure, whichever occurs first. Subjects will return to the participating institution for a 30-day follow-up visit followed by a 12-month vital status/survival status check. The 12-month vital status/survival status check may be conducted via a phone call if an in-office visit is not feasible. [REDACTED]

An independent Clinical Events Committee (CEC) will be utilized to adjudicate key adverse events pertinent to the study's descriptive endpoints.

## Statistical Analysis Plan

### 1.4 Endpoints

The following descriptive endpoints will be reported using summary statistics and no hypothesis tests will be performed.

1. Evaluation of the VARC-2 event rates at 30 days from the index procedure
  - Cardiovascular Mortality
  - Myocardial Infarction
  - Stroke (including disabling and non-disabling)
  - Bleeding (life-threatening, major, minor)
  - Acute kidney injury
  - Vascular access site and access-related complications (major and minor)
  - Annular rupture
  - Conversion to open surgery
  - Coronary obstruction
  - Valve embolization
  - Transcatheter valve-in-valve deployment
  - Permanent pacemaker insertion

Additional analysis of predictors of VARC-2 events (e.g. PVL or new permanent pacemaker) may be conducted.

2. Delivery profile characteristics such as access vessel diameter, sheath utilization and sheath size
3. Implant success defined as:
  - Absence of procedural mortality
  - Correct positioning of a single Portico prosthetic heart valve into the proper anatomical location
4. Echocardiographic assessment of hemodynamic valve performance at 30 days compared to baseline for the subjects with Portico valve implanted.
  - Mean gradient
  - Effective orifice area
  - Paravalvular leak (PVL)(Core Lab adjudicated echocardiographic measures will be utilized for evaluating valve hemodynamic performance at 30 days)
5. Clinical improvement from baseline to 30 days for the subjects with Portico valve implanted assessed by:
  - New York Heart Association (NYHA) functional class
  - Quality of Life (QoL) questionnaire (EQ5D-3L)
6. All-cause mortality at 30 days and 12-months

## Statistical Analysis Plan

### 2 ANALYSIS CONSIDERATIONS

#### 2.1 Analysis Populations

[REDACTED]

#### 2.2 Statistical Methods

##### 2.2.1 Descriptive Statistics for Continuous Variables

For continuous variables (e.g., age, etc.), results will be summarized with the numbers of observations, means, and standard deviations, with median and range for the means.

##### 2.2.2 Descriptive Statistics for Categorical Variables

For categorical variables (e.g. gender, diabetic status, etc.), results will be summarized with subject counts and percentages/rates.

##### 2.2.3 Survival Analysis

Survival analysis will be conducted to analyze time-to-event variables. Subjects without events will be censored at their last known event-free time point. Survival curves will be constructed using Kaplan-Meier (KM) estimates.

##### 2.2.4 Analyses in Response to COVID-19 Impact

As the coronavirus disease of 2019 (COVID-19) pandemic has spread around the globe, the following analysis mechanism will be implemented to minimize the potential confounding effect from this emerging infectious disease for the trial endpoints set forth in final report. In alignment with the guidance document EU “Guidance on the Management of Clinical Trials during the COVID-19 (Coronavirus) Pandemic” updated 28-April-2020, additional consideration will be given to the impact of the COVID-19 pandemic on the endpoint analyses for this study. As such, prespecified methods are included in the sections that follow to indicate the handling of any outcomes impacted by COVID-19 as well as efforts to minimize missing endpoint data during the COVID-19 pandemic.

## Statistical Analysis Plan

### 2.3 Endpoint Analysis

All endpoints are descriptive and will be summarized as described below. No hypotheses tests will be performed. All analyses will be performed on available data and all applicable summary.

#### 2.3.1 Evaluation of the VARC-2 event rates at 30 days from the index procedure.

For each VARC-2 adverse event reported within 30 days of index procedure (i.e.  $0 \leq$  Number of days since index procedure  $\leq 30$ ), number of events, number of subjects with event and event rate will be provided.

Evaluation of all-cause Mortality is discussed in section 2.3.6.

#### 2.3.2 Delivery system profile characteristics.

Delivery system characteristics such as access vessel diameter, sheath utilization, sheath size, etc. will be presented as follows:

Continuous characteristics will be summarized using descriptive statistics including mean, standard deviation, median, and range. Categorical characteristics will be summarized using frequencies and percentages. For the estimation of percentages, all subjects in AP with available data will be evaluated.

#### 2.3.3 Implant success.

Implant success is defined as:

1. Absence of procedural mortality
2. Correct positioning of a single Portico prosthetic heart valve into the proper anatomical location

Each component of implant success will be summarized using frequencies and percentages.

#### 2.3.4 Hemodynamic valve performance at 30 days compared to baseline.

- Mean gradient
- Effective orifice area

## Statistical Analysis Plan

- Paravalvular leak (PVL)  
(Core Lab adjudicated echocardiographic measures will be utilized for evaluating valve hemodynamic performance at 30 days)

Paired and unpaired analyses will be implemented. Only available data will be used in the summary.

[REDACTED]

### 2.3.5 Clinical improvement from baseline to 30 days by assessment of:

- **New York Heart Association functional class**

NYHA Class will be summarized at Baseline and 30 days using frequencies and percentages. Additionally, paired analysis will be used to evaluate NYHA Class Improvement from Baseline to 30 days for all enrolled subjects in AP who have completed NYHA assessments at **both** Baseline and the 30-day follow-up.

- **Quality of Life (QoL) questionnaire (EQ5D-3L)**

All five dimensions captured on the EQ5D-3L questionnaire and Visual analogue score will be summarized at Baseline and 30 days using descriptive statistics including mean, standard deviation, median, and range. In addition, paired analysis will be used to evaluate QoL improvement from Baseline to 30 days for all enrolled subjects in AP.

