5.4.2 Portico Valve Implant or Index Procedure

The medical team performing the TAVI procedure will typically consist of:

- An implanting physician (either an interventional cardiologist or a cardiac surgeon) at the center who will perform the procedure
- A second operator (a cardiac surgeon or a cardiologist) may be present during the procedure as needed

- An anesthesiologist and a perfusionist as needed for their own functions

NOTE: Anticoagulation use is left to the physician's discretion or should be established as with any other biological valve implantation, considering risks and benefits for the patient.

The implant procedure will be conducted per standard of care guidelines at each center, and in accordance with the product IFU and Sponsor's training program. The procedure will consist of the following activities:

1. Adverse events assessment
2. Document transcatheter aortic valve deployment information
3. Procedural characteristics
4. Procedural imaging (angiogram, intra-procedural echocardiography assessments) if available as part of standard of care
5. Resource utilization assessment

It is recommended to follow the peri-procedural instructions for the assessment of aortic regurgitation and implant depth as mentioned in Appendix E: Peri-procedural Guidelines. However, an implant center may follow their own standard of care practices and failure to follow these instructions will not be considered a protocol deviation.

During the procedure, the implanting physician may determine the implantation of the Portico valve is either not feasible or not in the best interest of the patient. Reasons for procedural exclusion may include, but are not limited to, anatomy that is not suitable for implantation, inability to gain access, ventricular arrhythmia, or any other contraindication.

If the implant procedure was not attempted (i.e. the Portico delivery system was never introduced into the subject's vasculature), the subject will not be considered enrolled. Refer to Section 5.3: Point of Enrollment.

If the implant procedure was attempted (i.e. the Portico delivery system was introduced into subject's vasculature) but the Portico valve could not be implanted (e.g. Portico attempted but other valve ultimately placed in the annulus), the subject will be withdrawn from the study after a 30-day adverse event collection period.

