5.4.3 Pre-discharge Visit

The pre-discharge visit will take place at the time of hospital discharge or within seven days after the index procedure, whichever occurs first. If the patient is expected to be discharged over the weekend, the discharge tests may be completed on the last weekday prior to discharge. The assessment will include:

- Physical assessment
- Blood sample (Creatinine, Hemoglobin, Troponin, if available, as part of standard of care)
- Anti-platelet and anti-coagulation medication assessment
- Adverse events assessment
- Pacemaker dependency assessment (as applicable)
- Data on resource utilization will be collected to determine the costs associated with hospitalization for a Portico implant procedure

5.4.4 30 Day Follow-up Visit

Each patient will return to the participating institution for a follow-up visit at 30 days (30+90 days) post index procedure. The scheduled visit window is calculated from the date of implant procedure.

The following procedures must be completed at the 30-day follow-up visit:

- Physical assessment
- Blood sample (Creatinine, Hemoglobin, troponin) if available as part of standard of care
- Echocardiogram*
- NYHA functional status classification
- Completion of QoL questionnaire (EQ5D-3L)
- Heart rate and rhythm assessment
- Anti-platelet and anti-coagulation medication assessment
- Adverse events assessment
- Pacemaker dependency assessment (as applicable)

Sponsor Representatives may be involved in providing support during the follow-up procedures.

* Each site will be responsible for performing and interpreting the 30-day follow-up echocardiogram using the VARC-2 definitions. Echocardiograms will be sent to an independent Echocardiographic Core Laboratory for further analysis. Exams should be recorded in DICOM format and should be de-identified prior to sending to the sponsor.

5.4.5 12 Months Vital Status/Survival Status

Each patient will have a survival status check at 12 months (-7 days, +45 days) post index procedure. The scheduled visit window is calculated from the date of implant procedure. The vital status check will be performed to determine patient survival at 12 months only and may be conducted via an in-office visit or by telephone call with the patient during the visit window.

Every effort should be made to contact the subject for the 12 month vital status/mortality check. The subject should not be considered 'lost to follow-up' until:

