6.2 Analysis Population

The analysis population will include patients who undergo an attempted implant with the Portico valve. A subject is defined as having undergone an “attempted implant” if the Portico delivery system enters the subject’s body. Patients who do not undergo an attempted implant of the Portico device will be excluded from analyses.

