6.3 Descriptive Endpoints

The following descriptive endpoints are reported using only summary statistics and no hypothesis tests will be performed.

1. Evaluation of the VARC-2 event rates at 30 days from the index procedure
 - Cardiovascular Mortality
 - Myocardial Infarction
 - Stroke (including disabling and non-disabling)
 - Bleeding (life-threatening and/or disabling, major, minor)
 - Acute kidney injury
 - Vascular access site and access-related complications (major and minor)
 - Annular rupture
 - Conversion to open surgery
 - Coronary obstruction
 - Valve embolization
 - Transcatheter valve-in-valve deployment
 - Permanent pacemaker insertion
2. Delivery profile characteristics such as access vessel diameter, sheath utilization and sheath size
3. Implant success defined as:
 - Absence of procedural mortality at 30 days
 - Correct positioning of a single Portico prosthetic heart valve into the proper anatomical location

4. Echocardiographic assessment of hemodynamic valve performance at 30 days compared to baseline for the subjects with Portico valve implanted
 - Mean gradient
 - Effective Orifice Area
 - Paravalvular leak (PVL)(Core Lab adjudicated echocardiographic measures will be utilized for evaluating valve performance at 30 days)
5. Clinical improvement from baseline to 30 days for the subjects with Portico valve successfully implanted (implant success is defined in descriptive endpoint 3) by assessment of:
 - New York Heart Association functional class
 - Quality of Life (QoL) questionnaire (EQ5D-3L)
6. All-cause mortality at 30-days and 12-months

Valve hemodynamic performance, vessel size, implant depth and other continuous variables will be summarized using descriptive statistics including mean, standard deviation, median, and range. The remaining categorical variables will be summarized by frequency and percentage. Additional analysis of predictors of VARC-2 events (e.g. PVL or new permanent pacemaker) may be conducted.

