## 5 ACRONYMS AND ABBREVIATIONS

Acronym or Abbreviation	Complete Phrase or Definition
AE	Adverse Event
AP	Attempted Procedure
CEC	Clinical Events Committee
CIP	Clinical Investigation Plan
CRF	Case Report Form
IP	Implanted Population
KM	Kaplan-Meier
NYHA	New York Heart Association
SAP	Statistical Analysis Plan
SD	Standard Deviation

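### SAP 2.3.5 runs the paired endpoint 5 analyses in all attempted implants, although the endpoint is defined for implanted subjects, and SAP 2.3.3 plans no combined implant success rate

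*SAP*

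**What the plan says.** **Population for endpoint 5 (NYHA class and EQ-5D-3L).** SAP 1.4 words the endpoint as "Clinical improvement from baseline to 30 days for the subjects with Portico valve implanted assessed by" NYHA class and EQ-5D-3L; Protocol 4.3 has the same wording. Protocol 6.3 restricts it further: "for the subjects with Portico valve successfully implanted (implant success is defined in descriptive endpoint 3". In the analysis section, SAP 2.3.5 says for NYHA that "paired analysis will be used to evaluate NYHA Class Improvement from Baseline to 30 days for all enrolled subjects in AP", limited to those assessed at both visits. For quality of life it says that "paired analysis will be used to evaluate QoL improvement from Baseline to 30 days for all enrolled subjects in AP", without that limit. SAP 5 expands AP as Attempted Procedure and also lists an "Implanted Population" (IP), which no visible endpoint section uses. SAP 2.1, on analysis populations, is redacted.

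**Implant success (endpoint 3).** It has two components: no procedural mortality, and a single Portico valve correctly positioned. SAP 2.3.3 plans frequencies and percentages for each component. Protocol 6.3 puts a 30-day limit on procedural mortality; Protocol 4.3, Protocol Appendix B, SAP 1.4 and SAP 2.3.3 do not.

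**EQ-5D-3L.** SAP 2.3.5 summarises the five dimensions and the VAS together by mean, SD, median and range. Protocol 5.5 describes each dimension as having three levels. SAP 2.2.2 calls for counts and percentages for categorical variables. No statistic is named for the paired analyses.

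**The concern.** In a registry with no hypothesis tests, the denominator and the chosen statistic are the result. Followed literally, SAP 2.3.5 adds to endpoint 5 the subjects in whom the Portico valve was attempted but not implanted, whom the endpoint's own definition leaves out. A programmer working from SAP 1.4, SAP 2.3.5 or Protocol 6.3 could produce three different tables.

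Endpoint 3 is meant to be one rate per subject, and Protocol 6.3 uses it as a per-subject status to select the endpoint 5 group. If only the components are tabulated, neither the success rate nor the size of that group can be read from the report. The differing mortality wording means that a death after the procedure but within 30 days could be classified differently depending on the section followed.

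SAP 2.7 repeats every endpoint by delivery-system cohort, so any ambiguity carries into that presentation too.

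**Working it through.** The visible documents give no rate of failed implantation, visit attendance or improvement, and the sample-size rationale is redacted. There is no plan figure to reproduce. All rates below are assumptions for illustration; only the 1000 subjects (500 per cohort) come from the plan (Protocol 6.5).

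**1. Populations side by side**

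| Place | Endpoint 5 population |
|---|---|
| SAP 2.3.5, both paired analyses | all attempted (AP) |
| SAP 1.4, Protocol 4.3 | Portico valve implanted |
| Protocol 6.3 | implanted and meeting endpoint 3 |

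The sets are nested: each contains the one below it. AP therefore includes every subject the definition asks for, plus those not implanted.

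**2. Size of the population effect**

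Assume that a share q of 1000 attempted subjects is not implanted, that a share r of those attends the 30-day visit, that 85% of implanted subjects attend, and that 75% of implanted attendees improve. Let p be the share improving among non-implanted attendees.

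- Share of non-implanted subjects in the paired data: f = 1000qr / (1000qr + 1000(1 − q) × 0.85)
- AP minus implanted, proportion improved: f × (p − 0.75)

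| q | r | f | p = 0.75 | p = 0.25 | p = 0 |
|---|---|---|---|---|---|
| any | 0 | 0 | 0 | 0 | 0 |
| 0.01 | 0.5 | 5/(5 + 841.5) = 0.59% | 0 | −0.30 | −0.44 |
| 0.03 | 0.25 | 7.5/(7.5 + 824.5) = 0.90% | 0 | −0.45 | −0.68 |
| 0.03 | 0.5 | 15/(15 + 824.5) = 1.79% | 0 | −0.89 | −1.34 |
| 0.03 | 1 | 30/(30 + 824.5) = 3.51% | 0 | −1.76 | −2.63 |

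The last three columns are percentage points. On attendance, the Protocol points both ways. Section 5.4.2 says that after a failed attempt "the subject will be withdrawn from the study after a 30-day adverse event collection period", and section 5.4.4 schedules subjects "for a follow-up visit at 30 days (30+90 days) post index procedure", so the window opens only as that period ends. That points to few or no attendees. Sections 5.3 and 5.11, however, keep such subjects in follow-up for 30 days, so some may be seen.

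**3. Combined implant success**

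If the components are met by shares a and b, the share meeting both lies between max(0, a + b − 1) and min(a, b). With assumed a = 0.98 and b = 0.97:

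- lower bound: 0.98 + 0.97 − 1 = 0.95
- upper bound: min(0.98, 0.97) = 0.97

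That is 950 to 970 of 1000 subjects, or 475 to 485 of 500 in a cohort.

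**4. Paired change in an EQ-5D-3L dimension**

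Assume levels 1/2/3 at 30/55/15% at baseline and 45/47/8% at 30 days.

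- Baseline mean: 0.30 + 2 × 0.55 + 3 × 0.15 = 1.85
- 30-day mean: 0.45 + 2 × 0.47 + 3 × 0.08 = 1.63
- Median 2 at both visits (cumulative shares 0.30/0.85 and 0.45/0.92)

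The share improved is not determined by these margins:

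- It is at least 0.45 − 0.30 = 15%, because level 1 must gain that much.
- It is at most 0.15 + 0.45 = 60%: everyone leaving level 3, plus level 1 filled entirely from level 2.

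Both limits are attainable. By-visit tables in any format therefore cannot show improvement; the paired statistic has to be named.

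**The case against.** Several stronger readings are tempting, and the documents do not support them.

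- *Protocol 6.2 also puts endpoint 5 in attempted implants.* It says that "The analysis population will include patients who undergo an attempted implant with the Portico valve", but this is a general statement that names no endpoint. A general set narrowed by endpoint wording is ordinary drafting. The conflict lies in the endpoint-specific texts.
- *The SAP fails to define its populations, or leaves the by-visit summaries without one.* SAP 2.1 is redacted and may define AP and IP and assign them to endpoints. Only the visible AP wording in the two paired sentences can be held against the plan. That wording stands, because whatever 2.1 says, SAP 1.4 and 2.3.5 differ.
- *Endpoint 5 will be materially distorted.* Protocol 5.4.2 gives as an example a subject who receives another valve in the annulus; such subjects may improve as often as the rest, and then the effect is zero even with full attendance.
- *No implant success rate will be reported.* Protocol 6.3 lists implant success as an endpoint and has a general rule of frequency and percentage for categorical variables, which arguably covers it. SAP 3.3 also summarises terminations for unsuccessful implant. SAP 2.3.3 does not forbid the combined rate; it just does not plan it.
- *The EQ-5D-3L summary is missing.* It is stated. The list in SAP 2.3.5 is not worded as exhaustive, SAP 2.2.2 already covers categorical data, and mean and SD together determine three level proportions. Level counts are a matter of readability.

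What remains is the population mismatch, the unplanned combined rate in the SAP, the differing mortality time frame and the unnamed paired statistic.

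**Conclusion.** The point holds as a minor inconsistency. SAP 2.3.5 does not match the endpoint definition in SAP 1.4 and Protocol 4.3, and Protocol 6.3 gives a third version. SAP 2.3.3 leaves the combined success rate unplanned, and the components cannot recover it: the gap is up to 2 percentage points under the assumed 98% and 97%.

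The population effect is probably small. In the illustrated cases it runs from zero to 2.63 points, and the upper end needs 3% not implanted, all of them attending and none improving. Nothing here touches an error rate or the sample size.

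**What to change.** (a) In SAP 2.3.5, use the implanted population of SAP 1.4 and Protocol 4.3 for endpoint 5, keep AP as an optional supportive table, and align Protocol 6.3. Implanted is preferable to successfully implanted because the latter also conditions on the outcome of endpoint 3. Confirm that IP in SAP 2.1 carries this definition.

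(b) In SAP 2.3.3, add the per-subject implant success rate (both components met, denominator AP) beside the components. Use one time frame for procedural mortality across Protocol 4.3, 6.3, Appendix B and the SAP.

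(c) Of lesser weight: report EQ-5D-3L dimensions by level counts and percentages alongside the stated mean and SD. Give paired improved/unchanged/worsened tables for NYHA and each dimension, and mean change for the VAS, in subjects with both visits.

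The cost is wording in the two documents and a few extra tables. The data are already collected.
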